2.2.1 Assessment for Potential Study Products Drug-Drug, Drug-Device, Device-Device Interactions

This device does not interact with any drugs delivered to a patient. This device does not affect airflow to a patient while inside the device. This device does not contain a power source/electricity. This device has dedicated ports and flaps to accommodate instruments, cords or tubing required to perform the aerosol generating procedure. The device has the ability to connect to a suction system to evacuate aerosol contained within the device. This portion is still undergoing additional lab-based testing and suction set-up will be for simulation purposes only for this trial.

2.2.2 Clinical Adverse Event Profile

Anticipated adverse events (AEs) or adverse device effects (ADEs) associated with use of this device include, 1) injury to the patient subject (patient in ABCD) or user subject (healthcare provider), 2) patient subject claustrophobia. 3) patient subject anxiety, 4) difficulty performing intubation with or without requiring removal of the device. Serious adverse events (SAEs) or serious adverse device effects (SADEs) would include 1) major injury to the patient or provider. Unanticipated adverse device events (UADEs) would include device breakdown. Based on the pre-clinical simulations (intubation and CPR), there is a low risk of increased technical difficulty during intubation and the device remains firmly in place during chest compressions for CPR. There is minimal anticipated risk, as noted above, to the user subject or patient subject. The device will remain on a patient for the duration of an aerosol generating procedure and then for a defined period post-procedure to simulate aerosol evacuation.

2.3 Risk/Benefit Assessment

2.3.1 Known Potential Risks

Immediate Risks: There is still a risk of droplet or aerosol exposure to infectious agents, such as SARS-CoV2 (the virus causing COVID-19) with this device. This device does not eliminate that risk and does not replace current CDC guidelines for PPE during an aerosol generating procedure, proper donning, and doffing of PPE and hand hygiene. This device is intended for use *in addition to* recommended PPE during an aerosol generating procedure. Additional bench testing is ongoing to assess the efficacy of the device in containing aerosol and limiting aerosol escape.

There is a risk of device failure due to improper set-up or use of the device. There may be an increase in cognitive burden as a result of introduction of a new form of PPE which has been suggested previously as a source of risk in aerosol generating procedures¹². The weight of the device is **9 lbs** and there is minimal risk of

injury to the user or the patient during setup and use with the device. All training material (written and audiovisual) must be reviewed and the initial survey completed prior to initiating use of the device.

There may be some variability in user comfort performing an intubation with this device. Based on our simulations and completion of the necessary training, there is likely to be minimal risk of a qualified user having device-related issues with intubation. In the event that the user feels the device is impairing their ability to safely intubate the patient, the device can be quickly removed by releasing the safety strap connectors and taking the device off the bed and proceeding to intubate without the barrier in place.

There is a risk of contamination from the device during removal of the device from the patient. PPE should be worn during removal and cleaning/disposal of the device.

There is a small risk of claustrophobia or anxiety for those patients in the device. This is a likely to be a minimal risk and this will be assessed as part of this study. All patients will be monitored while in the device and if they request to be taken out of the device or display signs of increasing anxiety/claustrophobia, the device will be removed.

Long-range Risks: There is a risk of device failure over time. Specifically, failure at seams, hand port septums, or straps. The integrity of the device should be assessed after each use and any obvious defects should be documented and the device removed from use. The free plastic sheeting over the torso will be disposable to reduce risks of cleaning a large plastic sheet and risks of the sheet developing tears or becoming dislodged from the device with repeated use. The device should be inspected after use for any physical tears or breaks in the frame or in the canopy and stored such that physical damage is limited. Parallel testing will also be ongoing in the lab setting with the engineering team as an added layer of assessing device durability, biocontainment and aerosol evacuation to get a complete picture from both a clinical use and engineering perspective on the number of times the device can be used reliably for biocontainment and aerosol evacuation.

2.3.2 Known Potential Benefits

Immediate Potential Benefits: This device offers an immediate benefit of providing an additional physical barrier for added protection of healthcare workers during aerosol generating procedures. The self-sealing hand and instrument ports offer a modular approach for enhanced safety of a patient during an aerosol generating procedure by allowing for additional assistance, if needed, during an aerosol generating procedure. Having a physical barrier in addition to standard PPE for aerosol generating procedures may also provide healthcare workers with an added layer of comfort and protection that they are better protected against contracting COVID-19 or other infectious diseases transmitted through droplet or airborne particles. This may decrease anxiety with regard to performance of aerosol generating procedures and this could improve the overall quality of the procedure.

The option for continuous suction provides a benefit of continuous evacuation of aerosol from the device during a procedure. This also offers the ability to clear contaminated air from the chamber after completion of an aerosol generating procedure to reduce the potential risk of spread of aerosol throughout the room and additional contamination of individuals and surfaces in the room.

Long-range Potential Benefits: The multiple hand and instrument ports also allows this device to be utilized for additional aerosol-generating procedures beyond intubation such as extubation, delivery of a nebulizer treatment, and open suctioning of a tracheostomy for a COVID19-treated patient. It may be feasible to use this

device for an extended period of time with positive pressure non-invasive devices such as a CPAP, BiPAP, or hiflow nasal cannula. The device in current form or with modifications outside the scope of this trial may also be useable for bronchoscopy. Use of these devices may allow for further adjustments to patient interaction protocols and allow for improved patient-care provider contacts which can enhance the quality of care and perceived level of care received by patients. There may be a long-term benefit of reduced healthcare worker risk of contracting COVID-19 or other droplet or airborne infectious diseases, which will allow for a long-term reduction in strain on the healthcare workforce by enhancing safety and wellbeing of frontline healthcare workers.

2.3.3 Assessment of Potential Risks and Benefits

The study subjects for this trial of a biocontainment device for aerosol generating procedures are frontline healthcare workers. The device is placed on top of a patient. The closest equivalent to this device is a face shield worn by a healthcare worker, which would provide no added significant risk to a patient for any procedure. This secondary “face shield” is placed over the patient as an added layer of protection during high risk procedures for generation of aerosols. Based on the results in Section 2 above, the preclinical risks of the device interfering with intubation, the most high-risk aerosol-generating procedure under investigation in this study, are small, but potentially could be serious if they occurred. **The primary goal of this study is to assess use of the device for planned airway procedures involving general anesthesia to better assess the feasibility for using this device as part of aerosol-generating procedure protocols for patients with highly transmissible (airborne or droplet) infectious diseases (i.e. COVID-19).** The benefits of this device are adding an additional layer of PPE protection for high risk aerosol generating procedures that has the potential to reduce risk of contracting COVID-19. There is also a potential benefit of containment of infectious aerosols to reduce contamination of surfaces and equipment in rooms where aerosol generating procedures are performed which may help streamline patient care, workflow and sanitation procedures long-term.

Risk of injury to a study subject or patient from this device is minimal. The device is lightweight, sturdy with good optical clarity for performing aerosol generating procedures. Below is a breakdown of major risk/failure points and steps taken to mitigate and assess risk by topic.

Environment:

1. *Site or sub-site location for device use.* There is a future risk of non-uniform device use due to cultural and environmental differences among units and hospitals where the device will be used. The initial study will involve two sites that are in close physical proximity, work closely together and are part of the same health system (HUP and PPMC) which will help inform appropriate changes to the label/user manual for device use.
2. *Situation Urgency/Emergency:* Extubation and delivery of a nebulizer treatment or suctioning are all accomplished in an orderly and timely fashion. Intubation, depending on the urgency requires a highly coordinated and efficient response and a new device may create another layer of risk by introducing another step in the intubation process. The process for device utilization will require a work flow where the provider performing/assessing the need for intubation can understand the potential risks/benefits of proceeding with intubation. **The primary goal of this study is to assess use of the device for planned airway procedures under general anesthesia to better assess the feasibility for using this device as part of aerosol generating procedures for COVID-19 patients.**

People:

1. *Human Error:* Human error is the largest risk factor for proper use of the device. Error in understanding device function, device setup, or aerosol evacuation could lead to a false sense of security in use of the device. Improper device utilization also has a risk to cause harm to the study subject. For this reason, there is a robust audiovisual and written/pictorial training program for device use with a plan for assessment of device training. An additional goal of this study will be to assess number of device uses needed to obtain proficiency.
2. *Clinical Training and Experience:* Study subjects will have a wide range of experience and training. The goal of this study is to involve stakeholders with multiple years/levels of experience in intubation procedures. We intend to track outcomes based on these variables to assess for further needs for enhanced training, healthcare burden, and overall device utilization.
3. *Patient Risk:* There is a small risk of mild patient injury with the device as well as a mild risk of claustrophobia or anxiety to the patient in the device. Patient injury from the device, small risk of abrasion or contusion if the patient sits up inside the device is unlikely to occur, and would be an adverse event if it were to occur. The preclinical feasibility indicates that the most technically challenging procedure of intubation can be performed safely with this device. All patients will be monitored while in the device and if they request to be taken out of the device or display signs of increasing anxiety/claustrophobia, the device will be removed.

Materials:

1. *Supply Chain:* Failure to secure a reliable supply chain for disposable elements of the device could result in inability to use device to fullest capacity and reduce effectiveness of protection against droplet and aerosol. Goal is to ensure reliable inventory of disposable components by keeping accurate logs of device use and remaining supplies, have an accurate estimate of need and burn rate for supplies and give manufacturing partner(s) adequate lead time for all components to be produced, shipped, and deployed in a timely fashion.

Methods:

1. *Device availability:* Each site/sub-site that is part of the study will have a designated storage location for units and associated disposable equipment. Given the restrictions on non-clinical staff in the hospital at this time, research coordinators/team members will not be onsite to bring equipment from storage to the room. The study PIs or subIs or study users will bring the device and associated components to the room for the procedure.
2. *Inability to perform intubation:* There is a small risk of inability to perform intubation with this device. The device has been designed to optimize hand positioning and mobility to triangulate the hands toward the patient's airway. The device safety straps have a quickly release function to rapidly remove the device and proceed with intubation if needed in the event the user has difficulty performing an intubation with the device in place.

Equipment:

1. *Device Failure:* Failure of the device is another potential source of risk. Device failure comes in multiple forms including structural failure due to repetitive use, damage during transport, damage during storage, manufacturing defects, damage during shipping. The design of the device has been simplified extensively to reduce the number of potential moving parts and structural failure points. The frame of the device also should not be susceptible to failure from repetitive cleaning over the course of the study period. To track any issues with a device, each device will have a unique identifier number that will be recorded on the Quality Use Survey with each device use. Devices will be inspected after being cleaned prior to storage for any signs of failure. The hand and instrument ports as well as the torso drape are additional point of device failure from repetitive use. The torso drape is a single use item that can be easily disposed of in a biohazard waste bin. The hand ports, frame and siding will be monitored and if signs of device failure/breakdown, the device will be logged as broken and taken out of circulation.

3 STUDY OBJECTIVES AND ENDPOINTS

The objectives of this study are to evaluate efficacy of training and use by frontline healthcare workers of a biocontainment system that provides additional protection during aerosol-generating procedures with COVID-19 patients. The primary objectives of this study are: 1) Assess changes in airway procedure times with and without the biocontainment device as a function of repeated utilization and as a function of patient-associated airway factors (Mallampati score, hyomental distance, neck mobility, BMI) and user-associated airway factors (experience of user, airway device used, induction sequence) and 2) Assess adverse events, adverse device events associated with biocontainment device use. Secondary objectives include: 1) Assess the subject's comfort with using the biocontainment device, 2) Assess for additional healthcare and cognitive burden imposed by the device. 3) Survey of patient's post-procedure on experience being inside the device. Exploratory objective includes gathering specific feedback regarding possible design modifications for further iterations and design improvements with the engineering team.

OBJECTIVES	ENDPOINTS	JUSTIFICATION FOR ENDPOINTS
Primary		

 1. Assess changes in airway procedure times with and without the biocontainment device as a function of repeated utilization and as a function of patient-associated airway factors (Mallampati score, hyomental distance, neck mobility, BMI) and user-associated airway factors (experience of user, airway device used, induction sequence). 2. Assess adverse events, adverse device events associated with using the biocontainment device. 	
 1. Measuring the time for performing an airway procedure with the biocontainment device when accounting for patient and user-specific factors. Sub-analysis, based on user experience level. 2. Quantifying the number of AEs or ADEs over time to assess device safety. Breakdown of AEs/ADEs as a function of time and by user subject. 	These endpoints were chosen to assess the safety and efficacy of biocontainment device use over time. This will help assess the viability of the device as an additional layer of protection for aerosol-generating procedures.
Secondary		

 1. Assess the user subject's comfort with using the biocontainment device. 2. Assess for additional healthcare and cognitive burden imposed by the device. 	
 1. Median Likert ratings from device use survey questions that assess user subject device comfort. 	These endpoints will provide additional information on the perceived quality of the device relative to

OBJECTIVES	ENDPOINTS	JUSTIFICATION FOR ENDPOINTS
Survey of patient's post-procedure on experience being inside the device	2. Median Likert ratings from device use survey questions that assess user subject healthcare burden with the device. Sub-analysis based on user experience level 3. Median Likert rating of the patient questionnaire results to assess patient experience in the device.	increased healthcare burden for frontline healthcare workers as well as any perceived patient discomfort.
Exploratory		
1. Assess feedback on device for iterative engineering and design improvements	Obtain broad feedback from end users on device use, function and design. Take information back to the engineering team for further design iterations or offshoots for other aerosol generating procedure applications.	To provide feedback for further device improvement and future projects.

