Airway procedure and patient data collection: Patient data and data from the anesthesia data record will be collected by PIs or their qualified designee post-airway procedure. As a result of social distancing and minimizing personnel due to COVID-19, it may not be possible to have a member of the research team present to observe and record data from each procedure. The airway procedures will be recorded using a GoPro camera placed in a fixed position. Data from the memory card will be transferred to an institutionally secured and managed network drive. Device use data will be collected from the videos by the PI or qualified designee. This data will include length of time to setup the device, length of time to perform the airway procedure, length of time to remove the device, number of times hand ports were used per procedure, and positioning of the torso drape. Patient data collected from the medical record will include patient demographics, contact information (phone and email), age, gender, race, co-morbid conditions (i.e. cardiac disease, lung disease, diabetes, BMI), smoking status. Airway procedure-related data that will also be collected will include BMI, hyomental distance, Mallampati score, type of airway procedure performed, number of attempts to perform the airway procedure, devices used for airway procedure, use of mask ventilation, anesthesia sequence used, and experience level of person performing the airway procedure.

Quality Use Survey and Safety Data Collection: As part of the study, user subjects will complete a Quality Use Survey after each day using the device. The results of the survey will be transferred from hard copies or REDCap to electronic format in CTMS for storage. This survey will collect user information on device functionality, perceived benefit of device use, healthcare burden associated with the device and safety data associated with device use. Safety data collected will include: 1) injury to the patient subject (patient in ABCD) or user subject (healthcare provider), 2) healthcare provider perceived patient subject anxiety or claustrophobia, 3) difficulty performing intubation with or without requiring removal of the device, 4) observed device defects or failures (i.e. broken strap, crack in plexiglass, break in hand ports).

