9.4.2 Analysis of the Primary Efficacy Endpoint(s)

Primary Endpoints:

1. Assessment of time to complete an airway procedure with or without the biocontainment device. The time is measured as a single quantitative measure at the end of the procedure. The initial starting time (T0) is defined as “time the mask is removed from the patient just prior to initiation of the airway procedure”. End time (T1) is defined as the time that the airway procedure is completed with a secure airway defined as the

time the airway device is secured to the airway circuit. Data will be presented as median amount of time for a given procedure with or without the biocontainment device and statistical significance will be determined by analysis of variance (ANOVA). Additionally, a multiple regression model will be created using covariates of subject user experience, number of prior uses with the device, and patient specific factors (co-morbid conditions, BMI, Mallampati score). This will help determine the critical factors associated with time to use the device.

2. The total number of AEs and ADEs will be presented. This will be broken down by specific AE or ADE. Logistic regression will be used to assess possible contributing factors to AEs or ADEs including subject user experience, airway procedure performed, patient-specific factors (BMI, co-morbid conditions, Mallampati score). We anticipate a low number of AEs/ADEs and as such, statistically rigorous regression analyses may be limited by a low overall number of events.

Statistical analyses will be performed on all data points, however, a sub-analysis will be performed on participants without any missing data points.

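### Primary objective 1 names neck mobility, which is neither listed for collection nor modelled, and hyomental distance, which is collected but left out of the planned regression

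*Combined protocol and SAP*

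**What the plan says.** Three parts of the plan bear on this point.

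- **Objective (section 3, repeated in the section 1.1 synopsis).** Procedure time with and without the device is to be assessed against repeated use, "patient-associated airway factors (Mallampati score, hyomental distance, neck mobility, BMI") and "user-associated airway factors (experience of user, airway device used, induction sequence"). That is four patient factors and three user factors.
- **Data collection (section 8.1).** "Airway procedure-related data that will also be collected will include BMI, hyomental distance, Mallampati score" opens the list of airway items. It continues with procedure type, number of attempts and devices used, and ends with "use of mask ventilation, anesthesia sequence used, and experience level of person performing the airway procedure". Neck mobility is not on it.
- **Analysis (section 9.4.2).** For device against no device, "statistical significance will be determined by analysis of variance (ANOVA"), with no covariates stated. In addition there is a multiple regression with "covariates of subject user experience, number of prior uses with the device, and patient specific factors (co-morbid conditions, BMI, Mallampati score"). Its stated purpose is to find which factors drive the time.

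**The concern.** A primary objective that lists its factors by name should be matched by a data list that captures them and a model that uses them. Here the three lists differ.

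The difference matters most for neck mobility. Under section 8.1 a patient's on-site participation is limited to the scheduled procedure, and under section 10.1.8.1 the videos are deleted within 14 days. An examination finding that was not recorded may therefore be unrecoverable.

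For hyomental distance the data will exist, but the model does not call for them. Adding the term later would be a post hoc choice in an unblinded trial whose time endpoint is analysed every two weeks (section 9.1).

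**Working it through.** The plan gives no figure on this point. The section 9.2 sample size (3.8416 × 0.25 / 0.01 = 96.04, rounded up to 97) uses no covariate information, so nothing below changes it. The check is mainly a comparison of lists.

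**Step 1. Set the lists side by side.**

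| Factor in primary objective 1 | Listed for collection (8.1) | In time regression (9.4.2) |
|---|---|---|
| Mallampati score | yes | yes |
| BMI | yes | yes |
| User experience | yes | yes |
| Hyomental distance | yes | no |
| Neck mobility | no | no |
| Airway device used | yes | no |
| Induction sequence | yes | no |

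Three of the seven factors are in the regression, and 7 − 3 = 4 are not. Of those four, three are collected and one is not listed.

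**Step 2. Look in the other direction.** The regression also has number of prior uses, which matches the repeated-use part of the objective, and co-morbid conditions, which the objective does not name. Randomised arm is not among its listed covariates, although the objective concerns times with and without the device.

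**Step 3. See whether another section closes the gap.**

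- Section 9.4.1 promises descriptive statistics on intubation-related factors and airway device, and has an open-ended sentence on covariates. It does not name neck mobility or specify a model for any of the four factors.
- Section 9.4.6 names gender, age, co-morbid conditions and years of experience as subgroups.
- Section 4.1 refers to section 9.4.7 for stratification, but section 9.4.7 only provides for listings of individual data.
- The schedule of activities (section 12.1) has a baseline data row that is not itemised.

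None of these closes it.

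**Step 4. Separate baseline factors from possibly post-allocation ones.** Hyomental distance and neck mobility are patient characteristics that allocation cannot change. Section 6.2.4 leaves the airway technique to the attending and describes that step after device assembly. Airway device and induction sequence may therefore be chosen with the allocation known, and adjusting for them could absorb part of the device effect. The same caution applies to airway procedure type, which is in the adverse-event logistic model but not in the time regression.

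**Step 5. Ask whether the precision effect can be sized.** With 100 device and 50 control procedures, the standard error of the arm difference in a model containing arm, in residual-SD units, is √(1/50 + 1/100) × √(1 − R²). Here R² is the share of residual variance that the added factors explain. At R² = 0 this is 0.173. The documents give no R². Assumed values of 0.02, 0.10 and 0.30 multiply the standard error by 0.990, 0.949 and 0.837, which are falls of 1%, 5% and 16%. The range runs from negligible to useful, and nothing in the plan narrows it.

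**The case against.** The strongest reply is that this is an editing mismatch in a safety and feasibility study, and that three tempting inferences go too far. Each of the three corrections below is right.

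- *A reader might infer that the primary objective cannot be answered.* That holds only for neck mobility. Hyomental distance, airway device and induction sequence are all collected and could be modelled. Even for neck mobility, the section 8.1 wording is not exhaustive and data are also drawn from the anaesthesia record. The supportable statement is that it is not listed for collection, not that it will never be recorded.
- *A reader might infer that all four absent factors are wrongly left out of the model.* Two of them, airway device and induction sequence, are better kept out of the main adjusted model for the reason in step 4. What they lack is any planned analysis against procedure time.
- *A reader might convert the omission into lost patients, using 150/(1 − R²).* The documents do not support a figure. No R² is given. BMI and Mallampati score are already in the regression. Section 5.2 excludes known and anticipated difficult airways, which narrows the range of the omitted factors. The device test is the ANOVA with no stated covariates, so extra terms in the separate regression would not sharpen it.

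What the reply does not remove is that the plan commits to two named patient factors in a primary objective, and nothing in it obliges anyone to record one of them or model the other.

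**Conclusion.** The mismatch is real and limited in size. Of seven named factors, three are modelled. Hyomental distance is collected but not modelled. Neck mobility is neither listed for collection nor modelled. Airway device and induction sequence are collected without a planned analysis against time. As written, the trial cannot report on neck mobility and would not model hyomental distance.

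The conclusion rests on reading section 8.1 and the section 9.4.2 covariate list as the operative commitments. It does not rest on any precision argument: a gain is possible but cannot be quantified from the documents. The validity of the randomised comparison is not in question. The change is worth making because it concerns a primary objective, costs little, and for neck mobility cannot safely wait until the data are in.

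**What to change.** 1. Before enrolment, add neck mobility with a defined grading to the section 8.1 data list, or delete it from the objective in sections 1.1 and 3. Either resolves the mismatch.
2. Add hyomental distance, and neck mobility if it is kept, to the pre-specified regression in section 9.4.2. Name randomised arm as a term in that model.
3. Report procedure time by airway device and by induction sequence descriptively or in a separate model, and say why they are not in the main one.
4. If airway procedure type is used as a covariate, use the type planned before randomisation.

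The cost is one extra baseline field (none if neck mobility is deleted) and a few model degrees of freedom out of 150 patients. The documents do not say whether neck mobility is already recorded in the routine airway examination, so the effort of collecting it should be confirmed with the sites.
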